9.2.6. JAKi Reporting Periods

For analyses evaluating changes in the use of tofacitinib according to updated recommendations in the JAKi 2022/2023 Article 20 referral, the indexing period will be split into the following 3 periods:

- **Reporting period 1**: which will cover the 63-month period after the initial distribution of the aRMM materials but prior to the PRAC/CHMP's notification of the JAKi referral (01 January 2018 through 31 March 2023, to allow for dissemination of DHPC letters);
- Reporting Period 2, which will cover the 5-month period after the PRAC/CHMP's notification of the JAKi referral, through initial distribution and uptake of the JAKi referral aRMM materials (01 April 2023 through 31 August 2023); and
- **Reporting Period 3**, which will cover the 16-month period after the period of initial distribution and uptake of the JAKi referral aRMM materials (01 September 2023 through 31 December 2024).

See Figure 5 for an overview of the JAKi Reporting Periods 1-3.

Figure 5. Overview of the JAKi Reporting Periods

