9.5. Study size

Comparative analyses for the changes in the proportions of patients with risk factors

For the comparative analyses, the study will assess changes in the proportion of tofacitinib initiators with risk factors of interest (e.g., VTE, elderly, CV, and malignancy) over different reporting periods (Section 9.2.4-9.2.6). The primary comparison of interest will be the proportion of tofacitinib initiators with risk factors during reporting period 3 (when full implementation of the updated aRMMs is expected) against that during reporting period 1 (baseline before implementation or notification of updated aRMMs). Secondary comparisons

b Data are updated once a year, usually by the end of August

of interest will be between reporting period 1 and reporting period 2, as well as reporting period 2 and reporting period 3 to assess any intermediate changes.

Sample size required for evaluating changes in the proportion of patients with risk factors across reporting periods was calculated using the following formula based on two independent sample *z*-test for proportions:⁸

$$N= \frac{(z_{\alpha/2}+z_{\beta})^2(p_1(1-p_1)+p_2(1-p_2))}{\epsilon^2}$$

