Preliminary data from the first interim report of the ongoing DUS study (A3921321) suggests that 30 to 80% of tofacitinib initiators had one or more risk factors of interest at baseline (e.g., during reporting period 1). Sample size was calculated across a range of possible baseline proportions and meaningful differences between any two reporting periods. Given the challenges in defining minimum meaningful differences and the lack of scientific guidance or validated thresholds, Chen et al.'s rule of thumb for classifying the magnitude of effect size based on odds ratios (OR) (e.g., small effect) is used to inform the minimum meaningful difference. Minimum sample size is determined based on the smallest sample size needed to detect a minimum meaningful difference per scenario of baseline proportion. It is thus estimated that 160 to 354 patients per reporting period (480 to 1,062 total patients) per indication group (e.g., RA/PsA and UC) are needed to detect a minimum meaningful difference with 80% statistical power ($\beta = 0.20$) and a two-sided 5% significance level ($\alpha = 0.05$) (Table 1**Error! Reference source not found.**). Sample size needed varies based on the baseline proportion and point percent difference between reporting periods. The required sample size is irrespective of the length of the reporting period.

Table 5.	Sample size for comparing changes in the proportion of patients with risk
	factors of interest across reporting periods

Percentage of patients with at least one risk factors at baseline	Point percent difference between any two reporting periods	Effect size classification for the difference based on OR ^a	Number of patients needed per reporting period ^b	Total number of patients needed for the entire study period per indication group b, c
80%	10%	Small	291	873
70%	10%	Small	354	1,062
70%	15%	Small	160	480
60%	10%	Small	385	1,155
60%	15%	Small	171	513
50%	10%	Small	385	1,155
50%	15%	Small	167	501
40%	10%	Small	354	1,062
30%	10%	Small	291	873

Odds ratio = VTE reporting period X odds of outcome / VTE reporting period Y odds of outcome; Classified effect sizes as weak ($1 \le OR < 1.5$), small ($1.5 \le OR < 2$), medium ($2 \le OR < 3$) and large (≥ 3).

Comparative analyses for the changes in composite risk factor scores

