For the comparative analyses that assess changes in the composite risk factor scores (e.g., mean number of risk factors per patient where each risk factor receives a score of 1) across reporting periods, the sample size was calculated using the following formula based on two independent sample *t*-test⁸:

$$N= \frac{2(z_{\alpha/2}+z_{\beta})^2\sigma^2}{\epsilon^2}$$

Preliminary data from the first interim report of the ongoing DUS study (A3921321) suggests the standard deviation for the mean number of risk factors per patient had a wide range but frequently centred around 0.6 to 0.8 at baseline (e.g., reporting period 1). Sample size was calculated across a range of standard deviations and differences in the mean number of risk factors per patient assuming equal sample sizes and variances between any two reporting periods. Given the challenges in defining minimum meaningful differences and the lack of scientific guidance or validated thresholds for the composite risk factor scores, Cohen's *d* effect size of 0.2 to <0.5 (small effect) was used to inform the minimum meaningful difference. Minimum sample size is determined based on the smallest sample size needed to detect a minimum meaningful difference per scenario of baseline variance. It is estimated that 80 to 142 patients per reporting period (240 to 426 total patients) per indication group (e.g., RA/PsA and UC) are needed to detect a minimum meaningful difference with 80%

^a References:^{9, 10}

^b Assuming equal sample size across reporting period

^c Bolded rows indicate minimum sample size required per scenario of proportions

statistical power (β = 0.20) and a two-sided 5% significance level (α = 0.05) (Table 6). Sample size needed varies based on the baseline variance and difference in the mean number of risk factors between reporting periods. The required sample size is irrespective of the length of the reporting period.

Table 6. Sample size for comparing changes in the mean number of risk factors per patient across reporting periods

Standard deviation for the mean number of risk factors per patient	Difference in the mean number of risk factors between any two reporting periods	Cohen's d effect size ^a	Number of patients needed per reporting period ^b	Total number of patients needed for the entire study period per indication group b, c
1.3	-0.20	Small	664	1992
1.3	-0.25	Small	425	1275
1.3	-0.30	Small	295	885
1.3	-0.35	Small	217	651
1.3	-0.40	Small	166	498
1.3	-0.45	Small	132	396

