1.3	-0.50	Small	107	321
1.3	-0.55	Small	88	264
1.2	-0.20	Small	566	1698
1.2	-0.25	Small	362	1086
1.2	-0.30	Small	252	756
1.2	-0.35	Small	185	555
1.2	-0.40	Small	142	426
1.2	-0.45	Small	112	336
1.2	-0.50	Small	91	273
1.1	-0.20	Small	475	1425
1.1	-0.25	Small	304	912
1.1	-0.30	Small	212	636
1.1	-0.35	Small	156	468
1.1	-0.40	Small	119	357
1.1	-0.45	Small	94	282
1.0	-0.15	Small	698	2094
1.0	-0.20	Small	393	1179
1.0	-0.25	Small	252	756
1.0	-0.30	Small	175	525
1.0	-0.35	Small	129	387
1.0	-0.40	Small	99	297

Table 6. Sample size for comparing changes in the mean number of risk factors per patient across reporting periods

Standard deviation for the mean number of risk factors per patient	Difference in the mean number of risk factors between any two reporting periods	Cohen's d effect size ^a	Number of patients needed per reporting period ^b	Total number of patients needed for the entire study period per indication group b, c
0.9	-0.15	Small	566	1698
0.9	-0.20	Small	318	954
0.9	-0.25	Small	204	612
0.9	-0.30	Small	142	426
0.9	-0.35	Small	104	312
0.9	-0.40	Small	80	240
0.8	-0.15	Small	447	1341
0.8	-0.20	Small	252	756
0.8	-0.25	Small	161	483
0.8	-0.30	Small	112	336
0.8	-0.35	Small	83	249
0.7	-0.15	Small	342	1026
0.7	-0.20	Small	193	579
0.7	-0.25	Small	124	372
0.7	-0.30	Small	86	258
0.6	-0.10	Small	566	1698
0.6	-0.15	Small	252	756
0.6	-0.20	Small	142	426
0.6	-0.25	Small	91	273
0.5	-0.10	Small	393	1179
0.5	-0.15	Small	175	525
0.5	-0.20	Small	99	297
0.4	-0.10	Small	252	756
0.4	-0.15	Small	112	336
0.3	-0.10	Small	142	426

- a. Reference:¹⁰
- b. Assuming equal sample size across reporting period
- c. Bolded rows indicate minimum sample size required per scenario of baseline variance

Through a preliminary assessment, the SNDS database holds records for approximately 4,000 RA or PsA patients and 1,000 UC patients who initiated tofacitinib between January 2018 (start of indexing period) and December 2020. It is projected that approximately 8,000

RA or PsA and 2,000 UC patients who initiate to facitinib will be captured through the end of the indexing period (e.g., December 2024).

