Based on these estimated numbers of patients during the entire study period and sample size calculation, the study is anticipated to have sufficient sample size to detect meaningful differences in the use of tofacitinib among patients with risk factors between the pre- and post-implementation period of updated aRMMs. All eligible patients during the study period will be included in the analysis. The number of patients will be actively monitored during the course of the study and the MAH will provide timely notification to the EMA if sufficient sample size is not reached during the planned study period.

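### Section 9.5 infers adequate size from a whole-study total and projects no count per reporting period; for UC, the stated 80% power then fails for the primary VTE contrast and for some JAKi contrasts

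*Protocol*

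**What the plan says.** Section 9.5 computes a number per reporting period "based on two independent sample *z*-test for proportions", with 80% power and "a two-sided 5% significance level". The result is 160 to 354 patients per period per indication group. Table 5 multiplies this by three, giving 480 to 1,062, under footnote b: "Assuming equal sample size across reporting period". The text adds: "The required sample size is irrespective of the length of the reporting period".

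For available patients, section 9.5 reports roughly "4,000 RA or PsA patients and 1,000 UC patients who initiated tofacitinib between January 2018" and December 2020, and projects 8,000 RA/PsA and 2,000 UC through December 2024. From these whole-study totals it concludes that "the study is anticipated to have sufficient sample size to detect meaningful differences in the use of tofacitinib" between the pre- and post-implementation periods. It also promises to monitor patient numbers and to notify the EMA if they are insufficient.

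Period 3 versus Period 1 is the primary comparison. Periods 1 versus 2 and 2 versus 3 are secondary. Sections 9.2.4 to 9.2.6 set period lengths of 17/17/50 months (VTE), 42/16/26 (CV and malignancy) and 63/5/16 (JAKi). JAKi Period 2 runs "01 April 2023 through 31 August 2023".

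**The concern.** Comparing three times an equal per-period n with a study total is valid only if patients divide about equally between periods. The calendar rules that out, and two further rules thin the UC group:

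- Section 9.2.2 excludes UC index dates before May 2019, while VTE Period 1 (section 9.2.4) ends on 31 May 2019.
- The JAKi outcome in section 9.7.2.5.1 is a proportion among UC patients with CV or malignancy risk factors, not among all UC starters.

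Section 9.7 analyses by indication group and declares significance at p < 0.05. A non-significant UC result could therefore be read as unchanged prescribing in an adequately sized study, when the contrast had little chance of showing a change that section 9.5 itself calls meaningful.

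**Working it through.** **1. The plan's own figure.** n = (1.960 + 0.842)² × [p1(1−p1) + p2(1−p2)] / (p1−p2)².

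- 70% to 60%: 7.849 × (0.21 + 0.24) / 0.01 = 353.2, so 354.
- 70% to 55%: 7.849 × (0.21 + 0.2475) / 0.0225 = 159.6, so 160.

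All nine rows of Table 5 reproduce exactly. The error is not in the per-period formula.

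**2. Expected UC counts.** The protocol gives no monthly accrual, so even accrual is assumed in two versions.

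- A: 1,000 over May 2019 to December 2020 (20 months, 50 per month), then 1,000 over 2021 to 2024 (48 months, 20.8 per month).
- B: 2,000 over the 68 months from May 2019 (29.4 per month).

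VTE Period 1 contains one eligible UC month: 50 (A) or 29 (B). VTE Period 3 holds 2 × 50 + 1,000 = 1,100 (A) or 50 × 29.4 = 1,471 (B).

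JAKi Periods 1/2/3 under A: 1,000 + 27 × 20.83 = 1,562; 5 × 20.83 = 104; 16 × 20.83 = 333. Under B: 1,382 / 147 / 471. Spreading 2,000 over all 84 indexing months puts Period 2 at 119.

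**3. Power at unequal n, same z-test.** Power = Φ( |p1−p2| / √[p1(1−p1)/n1 + p2(1−p2)/n2] − 1.960 ).

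Example: VTE, 50% to 40%, 50 v 1,100. The standard error is √(0.25/50 + 0.24/1,100) = 0.0722, and 0.10/0.0722 − 1.960 = −0.576, so power is 0.28.

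Ranges below cover the Table 5 baselines: 30–80% for 10 points, 50–70% for 15 points.

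| UC contrast | n | 10 points | 15 points |
|---|---|---|---|
| VTE P1 v P3 (primary), A | 50 v 1,100 | 0.28–0.40 | 0.55–0.62 |
| VTE P1 v P3 (primary), B | 29 v 1,471 | 0.19–0.27 | 0.36–0.42 |
| JAKi P1 v P2, A | 1,562 v 104 | 0.51–0.69 | 0.85–0.87 |
| JAKi P2 v P3, A | 104 v 333 | 0.43–0.57 | 0.77–0.81 |
| JAKi P1 v P2, B | 1,382 v 147 | 0.64–0.81 | 0.94–0.95 |
| JAKi P2 v P3, B | 147 v 471 | 0.57–0.72 | 0.89–0.92 |
| JAKi P1 v P3 (primary), A | 1,562 v 333 | 0.91–0.98 | >0.99 |

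Solving for 80% power against 1,100 in VTE Period 3, Period 1 would need about 79 to 237 UC patients, depending on the row.

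**4. The JAKi denominator.** The UC share with a CV or malignancy risk factor is not given. Borrowing the 30–80% any-risk-factor range of section 9.5, under A:

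- 30% share: Periods 1 and 3 hold 469 and 100; 10-point power is about 0.45–0.60.
- 80% share: 1,250 and 267; 10-point power is about 0.85–0.95.

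The baseline for this outcome (average daily dose above 10 mg) is not given either, so the Table 5 baselines are a second assumption.

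**5. RA/PsA.** 4,000/48 × 5 = 417 in JAKi Period 2, above the largest Table 5 requirement (385).

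**The case against.** Several stronger readings are tempting, and the documents do not support them.

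- A reader might set 104 against 160–354 and call the power lost. That range assumes equal groups. With Period 1 about 15 times larger than Period 2, the 70%-to-55% row that requires 160 still has power 0.85 for Period 1 versus 2.
- A reader might conclude that the whole study is underpowered. The sufficiency sentence concerns pre- versus post-implementation, and the Period 2 contrasts are secondary. On all UC starters the JAKi primary contrast holds, and RA/PsA in JAKi Period 2 is adequate.
- A reader might say the protocol dismisses period length. It says only that the required n does not depend on length, which is correct.
- For composite scores, 104 lies inside the stated 80 to 142 per period. With SD 0.6 and a difference of 0.20, power is 0.91 (Period 1 versus 2) and 0.84 (Period 2 versus 3).

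These limits stand, and the monthly counts are assumptions. They do not rescue VTE Period 1, where the primary UC contrast fails in every row under both accrual versions. Nor does the monitoring pledge settle the matter: sufficiency is argued from study totals, so UC could reach 2,000 and still leave that period nearly empty. The period had also closed well before this protocol version of February 2024.

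**Conclusion.** The sufficiency claim in section 9.5 does not follow from its own inputs, because available n per period is never projected. Three UC consequences follow under even accrual:

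- **VTE primary contrast:** clearly underpowered for both 10- and 15-point differences. This is the firmest result, since it follows from two dates in the protocol.
- **JAKi Period 2 secondary contrasts:** underpowered for nearly all 10-point differences. For 15 points, Period 1 versus 2 is adequate; Period 2 versus 3 is borderline at 104 patients and adequate at 147.
- **JAKi primary contrast in the at-risk subset:** anywhere from inadequate to adequate, depending on a share and a baseline that the protocol does not state.

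The finding does not extend to the JAKi primary contrast on all UC starters or to RA/PsA in JAKi Period 2. It should be corrected, but it does not threaten the study's descriptive aims.

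**What to change.** In section 9.5:

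- Replace the total column of Tables 5 and 6 and the sufficiency statement with expected n per period, reporting scheme and indication group, taken from SNDS counts where the period is already past. Include the at-risk UC subset for the JAKi outcome.
- Restate power, or the minimum detectable difference, at those unequal sizes, and limit the 80% claim to contrasts that reach it.
- Label the UC contrasts involving VTE Period 1 and JAKi Period 2 as descriptive, reported as an estimate with its confidence interval.
- Apply the monitoring and EMA notification check per period rather than to the total.
- Keep the sentence on required sample size and add that the available number does depend on period length.

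The cost is one table and some rewording. The stated power becomes less favourable; no extra patients or data are needed.

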9.6. Data management

Based on the extraction criteria provided by Certara France, the Caisse nationale de l'Assurance Maladie (CNAM) statisticians will search for patients within the SNDS and will develop the relevant targeting algorithm to meet this study's needs. After validation of this algorithm with Certara France, the CNAM will extract the data required for this study. As this is an extraction from the SNDS database, no specific data are collected from patients or doctors.

The data for the study will be made available to the Certara France project team in a dedicated project area on the SNDS portal (subject to the favourable opinion of the relevant committees). Only authorised Certara France users will be able to access data extracted from the portal. Certara France is committed to strictly respecting the benchmark determining the criteria of confidentiality, expertise and independence for research laboratories and design offices provided for by the decree of 17 July 2017.

The data will be kept for the number of years authorised for the conduct of the study and the publication of the results, then they will be permanently deleted.

The data will be received from SNDS in text format according to the selection criteria of the study. SAS® software (SAS Institute Inc., Cary, North Carolina, United States) or R or other appropriate analytical software will be used to process the data, including its management and analysis, manage the analytic datasets and conduct data analysis. This study will follow the relevant chapters of the European Network of Centres for Pharmacoepidemiology and Pharmacovigilance (ENCePP) and the International Conference on Harmonisation guidelines for data management. In addition, the data will be checked for consistency in terms of range of values, units of measurement and relevance of clinical information (e.g., a pregnancy diagnosis for a male patient).

9.7. Data analysis

Descriptive statistics will be provided for all results. Categorical variables will be reported using frequency distributions. Ordinal variables will be reported using frequency distributions, means, standard deviations (SDs), minimums, 25th percentiles, medians, 75th percentiles and maximums, unless otherwise specified. Continuous variables will be reported

using means, SDs, minimums, 25th percentiles, medians, 75th percentiles and maximums, unless otherwise specified. When relevant, 95% CIs will be calculated for the study outcomes outlined in Section 9.3.1 (Outcomes) and Table 3. All analyses will be stratified by the approved indication or indication groups ("RA or PsA" and "UC"), unless otherwise specified. In addition, for the objective of "Describe prescribing patterns over time", comparative statistical analyses will be conducted to describe changes in the use of tofacitinib across reporting periods to assess the statistical significance of reductions in the use of tofacitinib among patients with risk factors (see below for further details). P-value < 0.05 indicates statistical significance.

Missing values will be reported as missing and no imputation will be undertaken. Results will be summarised in tables and figures in Microsoft® Excel and/or Word format.

Detailed methodology for summary and statistical analyses of data collected in this study will be documented in a SAP, which will be dated, filed and maintained by the sponsor. The SAP may modify the plans outlined in the protocol; any major modifications of primary endpoint definitions or their analyses would be reflected in a protocol amendment.

9.7.1. Primary objective 1: Demographics, comorbidities and prior and current medications

The proportion of patients treated with tofacitinib with approved indications and off-label use will be described and tabulated.

The demographic, comorbid and medication variables listed in Table 3 will be described and tabulated in the relevant time period as specified. Additional stratifications may be considered during the SAP development, pending sufficient sample size.

9.7.2. Primary objective 2: Prescribers' adherence to the tofacitinib additional risk minimisation measures

9.7.2.1. Adherence to the recommended posology per indication and duration of use

Average daily dose, as listed in Table 3 and defined in Section 9.3.3, will be reported for each of the pre-specified time intervals as a continuous and categorical variable and may be stratified by presence of ≥ 1 major VTE risk factor(s) in the 12 months prior to tofacitinib initiation, pending sufficient sample size.

Duration of tofacitinib therapy, as listed in Table 3 and defined in Section 9.3.2, will also be described, tabulated and stratified by approved indication group ("RA or PsA" and "UC") and age (i.e., <65 and ≥65 years).

The variables listed under 'Outcome: Adherence to recommended posology' in Table 3 will be described and tabulated.

9.7.2.2. Adherence to patient screening and laboratory monitoring prior to and during tofacitinib treatment

The proportion of patients with evidence of having received the recommended screenings prior to initiation of tofacitinib and recommended monitoring after initiation of tofacitinib, as listed in Table 3, will be described and tabulated.

9.7.2.3. Adherence to recommendations for limitations of use

9.7.2.3.1. Potential contraindicated use of tofacitinib

The proportion of patients treated with tofacitinib with potential contraindicated use will be described and reported by type of contraindication, as follows:

Contraindicated use, as measured by:

- A patient *initiating* to facitinib therapy if they have severe hepatic impairment;
- A woman *initiating* to facitinib therapy if she is pregnant; 11, 12
- A patient *initiating* to facitinib therapy if they have or have had TB in the prior 2 months;
- A patient *initiating* to facitinib therapy if they have or have had a serious and/or opportunistic infection in the prior 2 months; and
- A woman *receiving* to facitinib therapy during her pregnancy. 11, 12
- Note that patients may be captured in more than one type of contraindicated use category.

9.7.2.3.2. Use with medications not compatible with tofacitinib

The proportion of tofacitinib patients with concomitant use of medications not compatible with tofacitinib will be reported overall and by patients with and without ≥ 2 tofacitinib prescription dispensing and measured by:

- The proportion of patients receiving biologics and/or potent immunosuppressants *while taking* tofacitinib; and
- The proportion of patients receiving a live vaccination while taking to facitinib.

Additionally, the number of overlapping days' supply of the biologic or selected potent immunosuppressant with the tofacitinib prescription dispensing will be summarised.

9.7.2.4. Describe prescribing patterns over time: Describe changes in the utilisation of tofacitinib following the updated recommendations and limitations for use implemented after the 2019 Article 20 referral and the 2021 signal evaluation procedure

